7.6 Other Reporting Requirements to Exelixis

o Pregnancy/Lactation Exposure

If a subject becomes pregnant during the study, she will be taken off study treatment and will be followed through the end of her pregnancy. Pregnancy (in subject or partner) or lactation exposure, although not an SAE, should be reported to Exelixis. Forms will be provided to the study sites upon request. The outcome of a pregnancy (for a subject or for the partner of a subject) and the medical condition of any resultant offspring must be reported to Exelixis. Any birth defect or congenital anomaly must be reported as an SAE, and any other untoward events occurring during the pregnancy must be reported as AEs or SAEs, as appropriate.

Medication Errors/Overdose

Any overdose, or study drug administration error that results in an AE, even if it does not meet the definition of serious, requires reporting within one (1) business day to Exelixis.

8.0 DRUG INFORMATION

8.1 Cabozantinib

A list of the adverse events and potential risks associated with cabozantinib can be found in Section 7.1.

Other names for the drug(s):

CABOMETYX COMETRIQ

Classification - type of agent:

Antineoplastic Agent, Tyrosine Kinase Inhibitor;
Antineoplastic Agent, Vascular Endothelial Growth Factor (VEGF) Inhibitor

Mode of action:

Cabozantinib is a potent inhibitor of proinvasive receptor tyrosine kinases (RTKs), including AXL, FLT-3, KIT, MER, MET, RET, ROS1, TIE-2, TRKB, TYRO3, and VEGFR-1, -2, and -3; induces apoptosis of cancer cells and suppresses tumor growth, metastasis, and angiogenesis

Storage and stability:

Store CABOMETYX at 20°C to 25°C (68°F to 77°F); excursions are permitted from 15°C to 30°C (59°F to 86°F)

Protocol dose:

40 mg daily continuous

Preparation:

N/A

Route of administration for this study:

Oral

Incompatibilities:

None

Availability:

Provided by supporter

Agent Ordering

Exelixis

Sub-site(s) will order agent through Exelixis and will receive the agent will ship directly to the sites.

Side effects:

The most commonly reported (≥ 25%) adverse reactions are: diarrhea, fatigue, nausea, decreased appetite, hypertension, palmar-plantar erythrodysesthesia (PPE), weight decreased, vomiting, dysgeusia, and stomatitis.

Agent Accountability

Accountability for the study drug at the study center is the responsibility of the Investigator. The Investigator will ensure that the study drug is used only in accordance with this protocol. Where allowed, the Investigator may choose to assign drug accountability responsibilities to a pharmacist or other appropriate individual.

The Investigator or delegate will maintain accurate drug accountability records indicating the drug's delivery date to the site, inventory at the study center, use by each patient, and destruction.

These records will adequately document that the patients were provided the doses as specified in the protocol and should reconcile all study drug received from Exelixis.

Study drug must not be used for any purpose other than the present study. Study drug that has been dispensed to a patient and returned unused must not be re-dispensed to a different patient.

Patients will receive instructions for home administration of cabozantinib according to the regimen description above. Cabozantinib is to be taken 1 hour before or 2 hours after meals. If doses of cabozantinib are missed or held, the patient should not make up for the missed doses.

Patients will be given a study medication diary to complete at home for cabozantinib. Compliance with the dosing regimen will be assessed based on completion of the drug diary and return of unused drug (or empty bottles).

IMP Destruction

IMP will be destroyed by the sponsor according to their SOPs. Destruction logs should be made available to Exelixis at the end of the study.

IMP Returns

Exelixis will not accept returned IMP

8.2 Pembrolizumab

A list of the adverse events and potential risks associated with Irinotecan can be found in Section 7.1.

- Other names for the drug(s): KEYTRUDA
- Classification type of agent:

Antineoplastic Agent, Anti-PD-1 Monoclonal Antibody;

Antineoplastic Agent, Immune Checkpoint Inhibitor;

Antineoplastic Agent, Monoclonal Antibody

Mode of action:

Pembrolizumab is a highly selective anti-PD-1 humanized monoclonal antibody which inhibits

programmed cell death-1 (PD-1) activity by binding to the PD-1 receptor on T-cells to block PD-1 ligands (PD-L1 and PD-L2) from binding. Blocking the PD-1 pathway inhibits the negative immune regulation caused by PD-1 receptor signaling[38]. Anti-PD-1 antibodies (including pembrolizumab) reverse T-cell suppression and induce antitumor responses.

- Storage and stability:
 - KEYTRUDA for injection (white to off-white lyophilized powder): Carton containing one 50 mg single-dose vial (NDC 0006-3029-02) Store vials under refrigeration at 2°C to 8°C (36°F to 46°F)...
 - KEYTRUDA injection (clear to slightly opalescent, colorless to slightly yellow solution): Carton containing one 100 mg/4 mL (25 mg/mL), single-dose vial (NDC 0006-3026-02) Carton containing two 100 mg/4 mL (25 mg/mL), single-dose vials (NDC 0006-3026-04) Store vials under refrigeration at 2°C to 8°C (36°F to 46°F) in original carton to protect from light. Do not freeze. Do not shake.
- Protocol dose:
 200 mg on day 1 every 21 days
- Preparation:
 Dilute in 50mL 0.9% Sodium Chloride IVPB
- Route of administration for this study: Intravenous infusion
- Incompatibilities: None
- Availability:
 Commercially available
- Agent Ordering
 Provided locally by the trial site
- Side effects:

Most common adverse reactions (reported in ≥20% of patients) were: KEYTRUDA as a single agent: fatigue, musculoskeletal pain, decreased appetite, pruritus, diarrhea, nausea, rash, pyrexia, cough, dyspnea, constipation, pain, and abdominal pain.

9.0 STATISTICAL CONSIDERATIONS

9.1 Study Design/Study Endpoints

This is a single-arm, open label, phase-II trial designed as a pilot to see if the treatment regimen is worthy of further study. Specifically, the trial is designed as the first stage of a Simon two-stage, minimax design[39]. The goal is to gather evidence on efficacy or futility of the study treatment in this study population, while monitoring toxicity. The two-stage approach offers economy and exposes the fewest possible participants to potential harm without substantial benefit, with control of the probability of errors in decisions.

Primary Endpoint: For efficacy the primary endpoint is progression-free survival at six months (PFS-6), dating from the first dose of study treatment. Progression is defined and determined as given in Section 61.6. For toxicity, the primary endpoint is the number of participants showing serious toxicity during their participation in the trial. Serious toxicities are given in Section 7.0.

Efficacy Null Hypothesis: Based on current outcomes for this study population[25][26], the null hypothesis is that 5% of evaluable patients will be progression-free at six months.

Efficacy Alternative Hypothesis: Based on our clinical judgment and aspirations, we anticipate that 20% (or more) of evaluable participants will be progression-free at six months. In our view, 20% progression-free at six months is the smallest advance that would be judged clinically worthwhile.

Secondary endpoints:

- Overall survival, defined as time from starting treatment to death from any cause.
- Objective response rate in patients with measurable disease as defined in section 6.0
- Safety as described in the adverse events in section 7.0

9.2 Sample Size and Accrual

Sample Size: Given null- and alternative-hypothesis proportions of 0.05 and 0.20, respectively, approximately 20 evaluable subjects will signal futility/efficacy with 80-percent power and five percent risk of type-I error. Under these conditions the table below gives the number of evaluable subjects required, the smallest number of patients progression-free at six months to signal efficacy, and the probability of correctly declaring futility.

Design Approach	Sample Size	Responses Signal Efficacy	Probability Correctly Asserting Futility
Minimax	19	>=2	0.75

As may be seen, the minimax approach requires 19 evaluable subjects for this project. If at least two participants are progression-free at six months, then the treatment regimen is considered worthy of further study. Given that result, then, in a separate study to complete stage two of the design, an additional eight evaluable subjects would be run. If at least four of the total of 27 evaluable were progression-free at six months that would be sufficient evidence to reject the null hypothesis of five percent in favor of the alternative hypothesis of 20 percent. The probability of declaring futility when in fact the null hypothesis (viz., 5%) is true is at least 75 percent.

No more than nine patients with PD-L1 CPS = 1-9% who are immunotherapy naïve will be enrolled.

Continuous Monitoring for Excess Toxicity: All participants in trial are monitored for serious toxicity for the duration of their participation in the study. Serious toxicities are given in Section 7. A sequential Pocock-type boundary will inform decisions to continue or stop accrual for excess toxicity, as accrual proceeds (Ivanova, 2005). The table below shows the cumulative number of participants enrolled and the corresponding cumulative number of serious toxicities that will signal the underlying risk of serious toxicity exceeds 33 percent (5% risk of type-1 error).

Threshold Number of Cumulative Toxicities that Signal Excess Toxicity as a Function of Cumulative Number Enrolled*

Cumulative	Threshold Number
Number	Showing Serious
Enrolled	Toxicity to Stop
	Accrual
1	-
2	-
3	-

CONFIDENTIAL

4	4
5	5
6	5
7	6
8	7
9	7
10	7
11	8
12	8
13	9
14	9
15	10
16	10
17	11
18	11
19	12
20	12

^{*} Pocock -type boundary with maximum acceptable probability of toxicity set to 33 percent and type-1 risk of five percent[40].

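### Section 9.2 ties 80% power and 5% type-I error to about 20 patients, but only the full 19-then-27 rule has them, and the protocol disagrees on whether patients 20 to 27 belong to this trial

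*Combined protocol and SAP*

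**What the plan says.** The hypotheses are the same throughout: 5% progression-free at six months under the null and 20% under the alternative (Study Summary, Statistical Methodology; Sections 9.1 and 9.2).

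On size and error rates, Section 9.2 states that "approximately 20 evaluable subjects will signal futility/efficacy with 80-percent power and five percent risk of type-I error". It introduces its table as giving, under those conditions, "the smallest number of patients progression-free at six months to signal efficacy". The single row shows a minimax design with 19 subjects, a cutoff of 2 or more, and a 0.75 probability of correctly asserting futility. The text below the table says that "the minimax approach requires 19 evaluable subjects for this project" and that, if at least two are progression-free, "then the treatment regimen is considered worthy of further study". Rejection of the null is kept for a later step, when "at least four of the total of 27 evaluable were progression-free at six months".

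On scope, Section 9.1 says "the trial is designed as the first stage of a Simon two-stage, minimax design", and Section 9.2 says that "in a separate study to complete stage two of the design, an additional eight evaluable subjects would be run". The Study Summary says otherwise. Its Number of Subjects entry allows up to 27, and its Statistical Methodology entry expands this trial's cohort to 27 after at least 2 successes in the first 19, then applies the test of at least 4 to the expanded cohort.

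The toxicity boundary in Section 9.2 has "maximum acceptable probability of toxicity set to 33 percent and type-1 risk of five percent". Its last printed row is patient 20.

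**The concern.** Two things do not fit.

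First, a power and a type-I error are attached to a size of about 20, and the table beside them labels 2 of 19 as a signal of efficacy. A reader could take 2 of 19 as a positive result at the 5% level. It is only a go/no-go look.

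Second, the sections disagree about where the trial ends. That decides whether eight patients, and the only 5%-level test of the primary endpoint, are in this protocol. Those who approve or monitor the trial cannot tell from the text which design they have before them.

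The size also has practical consequences. If 27 applies, toxicity monitoring has no thresholds for patients 21 to 27. Section 9.3 times the PFS-6 calculation only from the last patient enrolled. It gives no timing for the stage-one count and does not say whether accrual waits for it.

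**Working it through.** **Inputs.** p0 = 0.05 and p1 = 0.20 (Section 9.1). Stage one: 19 patients, continue if at least 2 succeed. Final rule: reject the null if at least 4 of 27 succeed (Section 9.2 and Study Summary). All calculations are exact binomial, with X ~ Bin(n, p).

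**The plan's own 0.75.** P(X ≤ 1 | 19, 0.05) = 0.37735 + 0.37735 = 0.7547. This reproduces. It is the chance of stopping at stage one under the null. Its complement, 0.2453, is the chance that an inactive regimen passes.

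**The claimed 5% and 80% at about 20 patients.** Type-I error is P(X ≥ r | n, 0.05) and power is P(X ≥ r | n, 0.20).

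| Rule | Type-I error | Power |
|---|---|---|
| ≥2 of 19 (tabulated) | 24.5% | 91.7% |
| ≥3 of 19 | 6.7% | 76.3% |
| ≥4 of 19 | 1.3% | 54.5% |
| ≥2 of 20 | 26.4% | 93.1% |
| ≥3 of 20 | 7.5% | 79.4% |
| ≥4 of 20 | 1.6% | 58.9% |

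No row has error at or below 5% together with power at or above 80%. A lower cutoff only raises the error, and a higher one only lowers the power. A search upward from n = 10 finds the first qualifying single-stage rule at n = 27 (≥4: 4.4% and 81.8%). A search of two-stage designs with futility stopping and a maximum of 10 to 27 finds none below 27.

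**The full rule.** Let X1 be the stage-one count and X2 ~ Bin(8, p) the stage-two count. Then

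P(reject) = P(X1 = 2)·P(X2 ≥ 2) + P(X1 = 3)·P(X2 ≥ 1) + P(X1 ≥ 4).

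- At 0.05: 0.17875 × 0.05724 + 0.05331 × 0.33658 + 0.01324 = 0.01023 + 0.01794 + 0.01324 = 0.0414.
- At 0.20: 0.15402 × 0.49668 + 0.21820 × 0.83223 + 0.54491 = 0.07650 + 0.18159 + 0.54491 = 0.8030.

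So the 5% (as a ceiling) and the 80% belong to the 19/27 rule.

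**Expected size.** 19 + 8 × 0.2453 = 20.96 under the null, and 19 + 8 × 0.9171 = 26.34 at 20%.

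**Toxicity table, relevant only if 27 applies.** An exact recursion with the printed thresholds at a true risk of 33% gives an overall crossing probability of 4.9% through patient 20, which agrees with the stated 5%. The table is therefore calibrated for about 20 patients. The plan does not state its pointwise level. A constant level of about 0.0186 reproduces the printed rows. If that level is assumed and carried on to patient 27, overall crossing becomes 5.7%.

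**The case against.** The strongest case on the other side is that the design itself is sound. The Study Summary and Section 9.2 give the same cutoffs, and on the 27-patient reading the promised error rates are met. The 24.5% is not hidden, because its complement is printed in both the table and the text. Section 9.2 calls 2 of 19 a reason for further study and does not claim that it rejects the null. Section 9.1 describes the trial as a pilot. The figure of about 20 may mean the expected size under the null, which is 20.96. The Study Summary makes expansion conditional on the first 19, which implies that patients 20 to 27 follow the stage-one result. The toxicity excess is under one percentage point and depends on an assumed way of extending the table.

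Much of this is fair. The 19/27 rule is not in dispute, the text below the table does soften the efficacy label, and for toxicity the missing rows matter more than the 5.7%.

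It does not rescue the sentence. The plan never mentions expected size, and even on that reading the error rates would belong to a rule that needs up to 27 patients. A one-sided normal approximation gives 22 (21.5 before rounding), but the exact rules at 22 also fail: ≥3 has 9.5% error and ≥4 has 66.8% power. Conditional expansion does not say whether accrual stops during the six months needed to count stage-one outcomes. Nothing in the objection resolves the conflict over scope.

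**Conclusion.** The concern holds in both parts and needs correcting.

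The error rates are attached to the wrong size. At 19 patients with the tabulated cutoff, the chances of a positive signal are 24.5% under the null and 91.7% under the alternative. The 4.1% and 80.3% that match the claim require the full 19/27 rule.

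The scope conflict is explicit, and the documents do not settle it. If the trial ends at 19, it has no test at 5% with 80% power. If it runs to 27, the size printed beside those figures is about seven too small (27 − 20), or one must assume that an expected size was meant.

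The efficacy figures rest only on the protocol's own rates and cutoffs and on independent patients, each counted as a success or failure at six months. The 5.7% for toxicity rests on the added assumption of a constant pointwise level.

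**What to change.** **Whichever size applies.** In Section 9.2, attach the 5% and 80% (exact 4.1% and 80.3%) to the 19/27 rule. Relabel 2 or more of 19 as the minimum to continue to stage two, in both the column heading and the sentence that introduces the table. The sponsor then decides whether this trial ends at 19 or 27 and aligns the Study Summary with Sections 9.1 and 9.2.

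**If 27.** Remove the wording in Section 9.1 that limits the trial to stage one, and the wording in Section 9.2 that gives 19 as this project's size and places the last eight subjects in a separate study. Extend the toxicity boundary to patient 27, calibrated so that overall crossing at 33% stays within 5%. This can be done by recalibrating at one constant level, which alters some printed rows, or by keeping the printed rows and choosing the added ones so that the total holds. State whether accrual pauses for the stage-one PFS-6 count and when that count is made.

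**If 19.** Change the Study Summary to 19. Report 24.5% (at 5%) and 91.7% (at 20%) as the chances of a go decision. Drop the 5%/80% claim and the efficacy label for this trial.

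**Cost.** A short amendment, with no patients beyond the 27 already in the Study Summary. Keeping 27 adds seven toxicity rows and a sentence on accrual. Keeping 19 means giving up the 5%/80% claim and stating a 24.5% chance of a false go.

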Operational Changes during the COVID-19 Pandemic	For the duration of the COVID-19 pandemic and in response to directives from the Vice Chancellor for Research and the UCI Human Research Protections Program, the Chao Family Comprehensive Cancer Center's Stern Center for Cancer Clinical Trials and Research will be modifying operations as outlined in Interim Standard Operating Procedure "Clinical Trial Enrollment and Operations during the COVID-19 Pandemic" dated 06April2020. In addition, the University of California Irvine Medical Center Pharmacy Services has issued guidance regarding the shipment of Investigational Drug Product directly to clinical trial participants when in-person clinic visits are not feasible or recommended. This new process is described in "Investigational Drug Services: Emergent Shipment of Investigational Product Policy" dated 23March2020. Current versions of these SOP and Policy documents may be obtained at the following URL: \hs.uci.edu\myshare\Cancer Center Research\COVID-19\Research\SOPs and Guidelines	
Methodology	Open label, single arm	
Study Duration	3 years	
Study Center(s)	Single Center	
Objectives	Primary objective: To estimate the efficacy of cabozantinib combined with pembrolizumab in patients with advanced gastric and gastroesophageal adenocarcinoma (GC) Primary Endpoint: 6 months progression-free survival (PFS-6) Secondary Objective: efficacy, safety, Secondary Endpoint: overall survival, objective response rate, adverse events	

Number of Subjects	Up to 27 subjects
Diagnosis and Main Inclusion Criteria	• Histologically proven unresectable or recurrent gastric or gastroesophageal adenocarcinoma • At least one prior chemotherapy regimen including a fluoropyrimidine and/or platinum agent • At least one line of treatment with a PD-1 or PD-L1 inhibitor in patients with PD-L1 CPS score >=10% • Age ≥ 18 years • Performance status (Eastern Cooperative Oncology Group) ≤ 2 • Adequate bone marrow function (ANC≥1000/mcL); and platelet count ≥ 60,000/mcL • Adequate liver function (total serum bilirubin level within normal institutional limits (or <3mg/dL in patients with Gilbert's disease) and serum transaminases ≤3xULN or ≤5xULN if liver metastasis is present); • Adequate renal function (serum creatinine level < 1.5xULN) • An expected survival period of>3 months • Patients with known MSI-High or dMMR tumors must have disease progression after at least one line of immunotherapy

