Study Product(s), Dose, Route, Regimen	Cabozantinib 40 mg p.o. daily days 1-21 Pembrolizumab 200 mg i.v. day 1 every 21 days
Study Duration	The study will consist of a screening period of up to 28 days, a treatment period (21 day cycles), and a follow up period of up to 18 months after enrollment of the last patient or until death, whichever occurs first. Subjects will be allowed to continue treatment on study until disease progression, unacceptable toxicity or withdrawal of consent.
Statistical Methodology	Main objective is to estimate the efficacy of the combination regimen with PFS-6 as a primary endpoint. The null hypothesis in this heavily pretreated population is a PFS-6 of 5%. The alternative hypothesis assumes a PFS-6 of 20% or more. A 2-stage approach will be used. If PFS-6 is seen in at least 2 out of the first 19 patients, the cohort will be expanded to a total of 27 patients. If the PFS-6 is achieved in at least 4 patients in the expanded cohort, that would be sufficient evidence to reject the null hypothesis of 5% in favor of the alternative hypothesis of 20% or more.

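### The toxicity stopping table ends at 20 enrolled, which fits Sections 9.1-9.2 but not the Study Summary's 27, and the event it counts is never named

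*Combined protocol and SAP*

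**What the plan says.** Section 9.1 states that "the trial is designed as the first stage of a Simon two-stage, minimax design". Section 9.2 requires 19 evaluable patients and says that, if at least two are progression-free at six months, "in a separate study to complete stage two of the design, an additional eight evaluable subjects would be run". The Study Summary gives the number of subjects as "Up to 27 subjects" and says that after a successful first stage "the cohort will be expanded to a total of 27 patients".

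For safety, Section 9.2 says "All participants in trial are monitored for serious toxicity for the duration of their participation in the study" and that "A sequential Pocock-type boundary will inform decisions to continue or stop accrual for excess toxicity, as accrual proceeds". The table gives thresholds for 4 to 20 enrolled (4, 5, 5, 6, 7, 7, 7, 8, 8, 9, 9, 10, 10, 11, 11, 12, 12), with a maximum acceptable rate of 33% and a type-I error of 5%. There is no row after 20.

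In Section 9.1, for toxicity, "the primary endpoint is the number of participants showing serious toxicity during their participation in the trial". Section 9.2 describes the table as giving "the corresponding cumulative number of serious toxicities that will signal the underlying risk of serious toxicity exceeds 33 percent". For what counts as serious toxicity, both sections point to Section 7 and say nothing more.

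**The concern.** A stopping rule needs a threshold for every patient it is meant to cover and an event that two people would count alike. The first holds only if the trial ends at stage one. If the Study Summary governs, the rule falls silent before the last patients enter. The second is open at any sample size. Serious toxicity is both the toxicity primary endpoint and the count that drives the rule, yet the reader cannot tell whether it means a serious adverse event of any cause, a drug-related grade 3-5 event, or something else. The same patients could then give different counts, and nobody could check whether 33% is a sensible limit for what is being counted.

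**Working it through.** **Inputs.** From Section 9.2: limit p0 = 0.33, overall type-I error 0.05, a look after every patient, and the printed thresholds. From Sections 9.1-9.2: 19 evaluable. From the Study Summary: 27. Assumptions: each patient's toxicity is known at enrolment, patients are independent, and true rates of 40%, 50% and 60% serve as examples.

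**1. Reproducing the table.** At each n, take the smallest t with P(X ≥ t | n, 0.33) ≤ c, where c is the largest constant that keeps the chance of ever crossing by the maximum N at or below 0.05. The crossing probability comes from an exact binomial recursion that removes each path once it reaches its threshold.

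- N = 20: c = 0.01855. All 17 printed thresholds are reproduced, and overall type-I error is 4.86%.
- N = 21: rows 4-20 and the 4.86% are unchanged.
- N = 19: row 8 would be 6 instead of 7.
- N = 27: rows 6, 10 and 12 would each be one higher.

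Used only to patient 19, the printed table has type-I error 4.69%. The calibration therefore fits stage one and does not fit 27.

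**2. Where the gap lies if 27 enrol.** A trial not stopped at n = 20 has at most 11 toxicities, so at most 12 at n = 21. Both extensions below require 13 at n = 21, so that row cannot trigger. The effective gap is patients 22-27.

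**3. Two ways to extend to 27.**

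- Recalibrated (c = 0.0163): 6 at n = 6, 8 at n = 10, 9 at n = 12; 13, 13, 14, 14, 14, 15, 15 at n = 21-27; overall type-I error 4.55%.
- Appended at the printed c: rows 4-20 unchanged; 13, 13, 13, 14, 14, 15, 15 at n = 21-27; overall type-I error 5.67%.

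**4. Chance of a stop signal by patient 27, all 27 enrolled.**

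| True rate | Printed | Recalibrated | Appended |
|---|---|---|---|
| 40% | 13.4% | 14.8% | 16.9% |
| 50% | 37.7% | 46.1% | 48.6% |
| 60% | 69.8% | 81.4% | 82.7% |

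**5. Allowing for the stage-two gate.** Stage two opens only if at least 2 of 19 are progression-free. The gate is G = 1 − (1−q)^19 − 19q(1−q)^18, which is 0.2453 at a six-month progression-free proportion (PFS-6) of q = 5% and 0.9171 at q = 20%. If efficacy and toxicity are independent, P(stop) = C19 + G × (C27 − C19), where Cn is the chance of crossing by patient n. Example, printed table at a 40% rate and q = 5%: 0.1265 + 0.2453 × (0.1337 − 0.1265) = 0.128.

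| PFS-6 | True rate | Printed | Recalibrated | Appended |
|---|---|---|---|---|
| 5% | 40% | 12.8% | 11.7% | 13.7% |
| 5% | 50% | 35.9% | 35.8% | 38.5% |
| 5% | 60% | 67.0% | 68.2% | 70.2% |
| 20% | 40% | 13.3% | 14.5% | 16.5% |
| 20% | 50% | 37.5% | 45.0% | 47.5% |
| 20% | 60% | 69.5% | 80.0% | 81.3% |

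Gated type-I error for the appended table is 4.9% at PFS-6 of 5% and 5.6% at 20%.

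**6. The counted event.** No arithmetic applies, so the texts are set side by side.

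- Sections 9.1 and 9.2: serious toxicity, by pointer to Section 7.
- Section 7.3: defines the serious adverse event, whatever its cause, and has death from progression reported as one. It does not define serious toxicity.
- Section 2.3: the safety endpoint is drug-related grade 3-5 events, up to four weeks after treatment.
- Sections 4.2 and 6.1.1: a patient is evaluable for toxicity once treated, and toxicity is assessed by CTCAE version 5.0.

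The start point and the general grading scale are therefore settled. The unit is largely settled too: Section 9.1 and the table's column heading count participants, and only the sentence introducing the table and its title speak of toxicities. What remains open is the attribution of the counted event and its grade or seriousness.

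**The case against.** The strongest reply is that the boundary has no fault. It fits the section that sets it out, and the missing rows follow only if the Study Summary overrides Section 9. That stands. A reader might infer that the table is miscalculated or that a safety gap is certain, and the documents support neither. The established fault is the contradiction over trial size; the gap is its conditional consequence.

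The gain from extending is also uneven. Near the 33% limit it is small: 13.4% to 14.8% at a 40% rate when recalibrated. With the gate at PFS-6 of 5%, recalibrating loses slightly at 40% and changes almost nothing at 50%. The figures are idealised as well, because the table is indexed on number enrolled while toxicity accrues throughout participation. All of this stands.

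The boundary also only informs decisions. Monitoring by the investigator and statistician and oversight by the DSMB (Section 10.5.2) would continue past patient 20. That limits the harm, but it supplies neither a threshold nor a definition.

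On the event, a reader might equate serious toxicity with the serious adverse event and conclude that the rule counts progression deaths and events before first dose. The documents never make that equation, and Sections 4.2 and 6.1.1 start toxicity at treatment. Section 2.3 offers another candidate, but Section 9 does not adopt it.

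**Conclusion.** The point holds as a conditional gap and an unnamed event, and should be corrected. The printed table is right for a maximum of 20 or 21, and if enrolment ends at 19-20 its length costs nothing. If 27 enrol under this protocol, there is no threshold after patient 20 (in effect for patients 22-27). The chance of a stop signal at true rates of 40%/50%/60% is then 13.4%/37.7%/69.8%, against 14.8%/46.1%/81.4% recalibrated or 16.9%/48.6%/82.7% appended. With the stage-two gate at PFS-6 of 5%, recalibrating brings almost no gain.

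These figures rest on toxicity being known at enrolment, on independence between patients and, for the gated values, between efficacy and toxicity, and on reading 33% as 0.33. With one third instead, the printed table's type-I error would be 5.13%.

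The missing definition applies at any sample size. Its effect on the counts cannot be sized from the documents, which give no serious-toxicity rate for this regimen and population.

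**What to change.** 1. **Settle the scope first.** Reconcile the Study Summary with Sections 9.1-9.2 on 19 versus 27. If the trial ends at stage one, keep the table and correct the Study Summary.

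2. **Only if 27 enrol here, extend the boundary to 27 and state its actual type-I error.** The choice is the sponsor's.
   - The recalibrated table of step 3 keeps type-I error at 4.5%. It weakens early detection: crossing by patient 10 falls from 21.3% to 12.9% at a 50% rate and from 42.8% to 28.5% at 60%. By patient 19 the loss is smaller (35.3% to 32.4%, and 66.1% to 63.9%).
   - Appending rows leaves stage one untouched and detects more, but 5.7% must replace the stated 5%.

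3. **Name the event.** Reconcile Sections 2.3, 7, 9.1 and 9.2 so that one named event is counted once per patient from first dose. State its attribution, its grade or seriousness, and whether deaths from progression count. Bring the sentence introducing the table and the table title into line with a count of patients. The sponsor should then confirm that the 33% limit suits that event.

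The cost is one scope statement, one definition and, only if 27 enrol, a longer table. No extra patients or assessments are needed.
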